2.6 Risks/Benefits

Very few adverse events been reported for diagnostic [18F]FES administration at the strength described for this study in 267 patients studied at the University of Washington. Patients have experienced pain and bruising at the injection site, and one patient reported a temporary slight change in taste. Thus few adverse effects are expected as a result of the administration of [18F]FES, except for discomfort at the injection site. The [18F]FES dose is slightly less than recommended safe oral dose assuming an oral conjugated estrogen dose of 2.5 mg in one day.

The IB also identifies potential risks, which have not been observed in patients receiving FES, but are theoretically possible based on the chemistry and pharmacology of FES: Tissue Injury, infection, extravasation of dose, allergic reaction, nausea, vomiting, anorexia, uterine bleeding, and secondary cancers due to radiation exposure.

FDG PET, blood draws, and biopsies are standard-of-care procedures. FDG PET has additional risks of pruritus, edema, and rash, occurring in less than 1% of patients. The blood draw may briefly cause patients to feel faint, lightheaded, nauseated, mild pain, bleeding, bruising and infection at the site of the needle insertion. Biopsies may cause pain, bleeding at the biopsy site, tenderness, scarring, or infection.

Carcinogenesis has not been observed in animal or clinical trials. Synthetic estrogens such as 2- fluoroestradiol and 4-fluoroestradiol are poor carcinogens in the same animal model systems because the fluorine blocks metabolism when substituted in these positions. [18F]FES is labeled with fluorine at the 16 position of the estradiol. Administration of [18F]FES as described herein, for up to four PET scan procedures, results in intermittent and vastly reduced overall estrogenic exposure compared to regimens known to cause cancer in animals.

FES imaging will not be used to direct therapy. It is not expected that patients on this trial will derive a benefit, this trial is intended only to expand the body of knowledge on FES imaging. The contribution to the body of knowledge for the use of FES is expected to far outweigh the minor risks of FES administration.

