6.2 Exclusion Criteria

- An inability to lie still for the tests
- Individuals weighing more than 300 lb. (this is the weight limit of the scanner table)
- Pregnant or lactating. Women of childbearing potential with either a positive or no pregnancy test at baseline are excluded.
- Any other life-threatening illness (e.g. serious, uncontrolled concurrent infection or clinically significant cardiac disease – congestive heart failure, symptomatic coronary artery disease, cardiac arrhythmia not well controlled with medication).
- Use of tamoxifen, faslodex, DES or any other ER blocking agent < 6 weeks or chemotherapy < 3 weeks prior to imaging scan.
- Unwillingness or inability to give informed consent.
- Uncontrolled diabetes mellitus (fasting glucose > 200 mg/dL)
- Adult patients who require monitored anesthesia for PET scanning.

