Day of [18F]FES PET/CT Scan: After the FES injection and rest period (section 6.6.1), the patient will be positioned supine in the PET/CT scanner. A low dose CT scan (60 mA) will provide attenuation correction data using non-contrast CT. The PET image acquisition sequence will be the same as that used for clinical FDG scans. This consists of a torso survey series of five-minute images acquired over 15 cm survey fields of view (FOVs) extending from the base of the skull to the mid thigh (5 to 7 FOVs in total). The images will be corrected for radioactive decay of the tracer and normalized to the injected dose and body weight. This results in regional standardized uptake values (SUVs) whole-body image sets.

Prior to injection, a whole blood sample may be taken for determination of albumin, estradiol and testosterone levels, heart rate and blood pressure will be recorded. A known quantity of nonradioactive FES will be added to plasma (from blood collected prior to injection) to determine binding to sex steroid binding protein (SBP). For patients in whom a second venous access line is feasible and has been placed, venous blood samples may be collected at 5, 20 and 60 minutes after injection of the [18F]FES for metabolite analysis in selected patients. Heart rate and blood pressure will be measured after the FES injection.

After the [18F]FES PET Scan: A follow up phone call will be made by study staff within 24 hours after the FES PET scan to ask about any signs of adverse effects. Patients will typically start the selected hormone targeted therapy within 30 days of the FES PET scan. Patients who have started aromatase inhibitors prior to [18F]FES PET will be permitted to enter the study, if an additional endocrine targeted treatment is planned.

In patients who consent to optional biopsies, a baseline tumor sample will be obtained after completion of the baseline PET imaging but prior to starting the selected endocrine targeted therapy. Where available and medically appropriate, a clinical or research biopsy that involved sampling of a relevant lesion within 6 months prior to the enrollment may be utilized in place of the baseline optional biopsy.

In some patients undergoing biopsies, a whole blood sample will be collected prior to starting the therapy, to allow correlation of steroid hormone levels in serum and biopsy tissue.

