Repeat FES PET scan and FDG PET scan: Patients will undergo a second FES PET and FDG PET scan after starting endocrine targeted therapy to assess the effect of therapy on ER expression and estradiol binding to the receptor. Exact timing of the second FES and FDG scans, will depend upon the endocrine targeted regimen and dosing, but typically will be 1 – 12 weeks after starting therapy.

The repeat FDG PET may be omitted in patients on SERD therapies, where repeat FES PET is used primarily to evaluate residual ER availability rather than tumor response. This will be determined by requirements of the co-enrolling companion therapeutic protocol.

Optional Biopsy: In patients who consent to optional biopsies, an early response tumor sample will be obtained 1-12 weeks after starting the selected therapy. This biopsy should take place after completion of the repeat PET imaging and should target the same tumor site as the baseline biopsy. A whole blood sample may be drawn for correlation of steroid hormone levels in serum and biopsy tissue.

Week 1 to 20 years after [18F]FES PET Scan: Clinical follow-up will continue for up to 20 years, time of progression and date of death will be recorded. For some patients, especially those receiving two endocrine-directed treatments, a third FES PET scan and additional research FDG PET scan may also be obtained 1-12 weeks after the second FES PET scan. For each patient, a maximum of 3 FES PET and 3 FDG PET scans would be done.

A study calendar is included in Appendix A.

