9.0 SUBJECT EVALUATION

9.1 On-Study Clinical Evaluations

To establish a baseline, this study plans to pull data from recent clinic visits for patients matching the eligibility criteria, if the visits occurred within the last 30 days. If one is not available, clinical evaluations will take place proceeding both the first and second FES scans (and the third, if applicable). These visits should occur as close to the FES scan as possible but must be within 30 days (+/-) of the FES scan. The following tests and procedures would be completed, although not all tests may be done at each visit;

- Physical Examination

- Vitals
- Labs:
 - Hematology: CBC, differential, platelets
 - Serum Chemistries: including calcium, magnesium, SGOT, SGPT, alkaline phosphatase, LDH, total bilirubin, BUN, creatinine, electrolytes, and glucose

Prior to FES administration, the following are completed:

- A whole blood sample may be taken (10mL) (optional)
 - A known quantity of nonradioactive FES will be added to plasma (from blood collected prior to injection) to determine binding to sex steroid binding protein (SBP).
- Heart rate and blood pressure

Following FES Administration, the following are completed:

- For patients able to have a second venous access, venous blood samples may be collected at 5, 20, and 60 minutes after collection.
- Heart rate and blood pressure

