11.0 SUBJECT DISCONTINUATION OF ACTIVE TREATMENT

Subjects may be removed from this study at any time at their discretion. Subjects may also be removed from this protocol if they develop any untoward side effects from the imaging product.

If a subject withdraws consent to participate in the study or aspects of the study, attempts should be made to obtain permission to record survival data up to the protocol-described end of the subject follow-up period. Survival data are important to the integrity of the final study analysis. Documentation in the medical record should state that the subject is withdrawing from the study and what, if any, selected data the subject will permit the investigator to obtain.

An explanation for discontinuing treatment is recorded for each subject discontinuing treatment in the study source. The Sponsor must be notified immediately if a subject discontinues treatment. All subjects, irrespective of treatment status, will continue to be followed for survival. Treatment in this study must be discontinued for any of the following reasons:

- if the Sponsor decides to stop the study;
- at Investigator's discretion;
- at the subject's request;
- if the subject enrolls in a trial of another investigational agent;
- Any adverse event possibly related to the IP, excluding mild pain, bruising, or controllable bleeding at the injection site
- pregnancy

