21.0 Appendix

Appendix A: Study Calendar

Baseline evaluations are to be conducted prior to administration of protocol therapy, typically within 30 days. Baseline FDG PET/CT scan will be obtained near the time of the [¹⁸F]FES-PET/CT scan, typically within 14 days. Procedures are outlined below:

	Pre-Study	Imaging 1	Rx 1	Imaging 2 ⁵	Rx 2	Imaging 3 ⁶	Follow up
Informed Consent	X						
Demographics	X						
Pregnancy Test ¹	X						
Vital Signs ²		X		X		X	
Research lab tests ³		X		X		X	
ER, PgR, HER2 ⁴	X						
FDG PET/CT ^{5,6,7}	X			X		X	
[¹⁸ F]FES injection and PET ^{5,7}		X		X		X	

Collect serum hormone levels ⁸		X		X		X	
Adverse Event Evaluation		X (0-24hr)		X (0-24hr)		X (0-24hr)	
Optional tumor tissue biopsy and blood draw ⁹		X		X			

¹If patient is pre-menopausal, and birth control use is not confirmed

²Vital signs include heart rate and blood pressure

³Additional blood tests to measure hormone levels (e.g. estradiol, estrone, testosterone, DHT, SHBG) or other hormone related measures might be performed in some patients depending on the treatment regimen.

⁴Pathology results from primary or metastatic biopsy will be reviewed and additional pathology tests may be performed on some patients depending on the treatment regimen.

⁵FES PET/CT and FDG PET/CT will be done at 1-12 weeks after the Imaging 1 time point depending on the treatment regimen.

⁶Repeat FDG PET may be omitted in patients on SERD therapies.

⁷FES PET/CT and FDG PET/CT may be done at 1-12 weeks after the Imaging 2 time point depending on the treatment regimen.

⁸Optional blood sample for estradiol, estrone, follicle-stimulating hormone, sex hormone binding globulin, testosterone and free testosterone serum levels.

⁹In patients consented to optional biopsies, obtain metastatic or recurrent tumor tissue from an FDG and/or FES avid site after completion of PET imaging but prior to start of the endocrine targeted therapy. Repeat the biopsy from the same site after 1-12 weeks on treatment. (Where available and medically appropriate, a clinical or research biopsy that involved sampling of a relevant lesion within 6 months prior to the enrollment may be utilized in place of the baseline optional biopsy.) A blood draw done during the same time point will accompany some biopsies.

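### Pregnancy requires discontinuation, but the calendar schedules a test only before the first scan, no section requires one before the repeat injections, and footnote 1 conflicts with exclusion criterion 6.2

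*Combined protocol and SAP*

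**What the plan says.** Section 11.0 states: "Treatment in this study must be discontinued for any of the following reasons". The last item on its list is pregnancy. Section 8.0 says that nothing is given under this protocol to treat the cancer, so here the rule can only govern the study imaging.

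On testing, Section 6.2 says: "Women of childbearing potential with either a positive or no pregnancy test at baseline are excluded". It makes no exception for contraception. In Appendix A the row "Pregnancy Test" has one mark, under Pre-Study. Footnote 1 to that row restricts the test to pre-menopausal patients for whom contraception has not been confirmed.

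On repeat imaging, a second FES scan is planned for all patients, with a second FDG scan that may be omitted under SERD therapy. For some patients, Section 8.1 (Treatment Plan Overview) adds that "a third FES PET scan and additional research FDG PET scan may also be obtained 1-12 weeks after the second FES PET scan". The ceiling in the same section is: "For each patient, a maximum of 3 FES PET and 3 FDG PET scans would be done".

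**The concern.** A rule that makes pregnancy a compulsory reason to stop works only if pregnancy is looked for before each exposure that it is meant to prevent. A negative test before the first scan says nothing about a pregnancy that begins in the following weeks or months. A site that follows the calendar to the letter could therefore give FES, a low-dose CT and, where repeated, FDG to a patient whom Section 11.0 requires to be discontinued.

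The stake is patient safety. Section 2.6 lists secondary cancers from radiation among the potential risks, and Section 13.2 counts harm to a fetus exposed in the study as a serious adverse event. Section 2.6 also says: "It is not expected that patients on this trial will derive a benefit". An avoidable exposure has no offsetting gain for the patient.

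The footnote raises a second problem, one of consistency. For a pre-menopausal patient with confirmed contraception, the calendar asks for no test, while Section 6.2 makes her ineligible if she has none. A coordinator who works from the calendar would create an eligibility deviation.

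**Working it through.** No sample-size, power or alpha figure bears on this point. The check sets the relevant sections side by side and adds up the calendar's scan windows.

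**1. Is there a pregnancy check anywhere after Pre-Study?**

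- Appendix A: vital signs, research labs, FES, FDG and adverse-event evaluation are marked at Imaging 2 and Imaging 3. The pregnancy row is blank there.
- Section 6.2: requires the test at baseline only.
- Section 8.1, Treatment Plan Overview: before the first scan, laboratory values for renal, blood and liver function are collected. On the scan day, the steps before injection are an optional blood sample, heart rate and blood pressure. The telephone call within 24 hours comes after the injection and asks about adverse effects.
- Section 8.1, Administration of IP: covers venous access, dose, vital signs and monitoring.
- Section 8.2, FDG: requires fasting and a glucose criterion.
- Section 9.1: lists physical examination, vitals, hematology and "Serum Chemistries: including calcium, magnesium, SGOT, SGPT, alkaline phosphatase, LDH, total bilirubin, BUN, creatinine, electrolytes, and glucose". Its steps before FES administration are an optional blood sample, heart rate and blood pressure.

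Result: none of these requires a pregnancy check at Imaging 2 or Imaging 3.

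**2. How far from Imaging 1 can the unchecked injections fall?** Calendar footnotes 5 and 7 give the windows.

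- Imaging 2: at most 12 weeks after Imaging 1.
- Imaging 3 (subset only): at most 12 + 12 = 24 weeks after Imaging 1.

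The Pre-Study test is older than this by a lead time that the calendar does not fix.

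**3. How many injections are concerned?** The ceiling is 3 FES and 3 FDG scans per patient.

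- Patient tested at baseline, no third scan: 1 repeat FES and 1 repeat FDG injection (FDG may be omitted under SERD therapy).
- Patient tested at baseline, with a third scan: up to 3 − 1 = 2 FES and 3 − 1 = 2 FDG injections.
- Patient to whom the footnote 1 waiver is applied: the first FES injection is also untested, so up to 3 FES injections. By Section 6.2 she should not have been enrolled.

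**4. Do footnote 1 and Section 6.2 agree?**

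| Pre-menopausal patient | Calendar footnote 1 | Section 6.2 |
|---|---|---|
| Contraception not confirmed | Test | Test needed for eligibility |
| Contraception confirmed | No test | Excluded if untested |

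They agree in the first row and conflict in the second. This takes the ordinary reading that contraception does not remove childbearing potential. The protocol does not define the term.

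**The case against.** The strongest reply is that other documents may cover the gap. Section 3.2 recruits from studies that already require an FES scan, and companion therapeutic protocols or routine PET-suite practice may include pregnancy testing. The schema figure and the consent pages are also not available here. This is fair as far as it goes. However, this protocol neither requires such testing nor refers to it, and Section 2.2 also allows patients whose therapy was chosen on clinical presentation rather than within a trial. The possibility is a reason to check the companion documents; it does not put a safeguard into this one.

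A second reply is that Section 11.0 is event-driven: it says what to do when pregnancy occurs, and other items on its list have no scheduled check either. That is true, and the list itself contains no error. The gap lies in Appendix A and Section 6.2. Pregnancy differs from, say, enrolment in another trial because it can go unnoticed, and a simple test before the injection can find it.

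A third reply concerns the baseline. A reader might infer from footnote 1 that women of childbearing potential will be enrolled untested. The documents do not support that. If Section 6.2 is applied, an untested woman of childbearing potential is excluded, and Section 6.1 separately requires patients not to be pregnant. What stands is a conflict between two written rules, which can lead a site into a deviation.

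Finally, a reader might want a negative test before every FDG injection. This protocol cannot impose that on the baseline FDG scan, which is normally standard care ordered by the treating physician and may have been done elsewhere before enrolment (Sections 3.3 and 8.2).

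**Conclusion.** The point holds on two counts. First, after the Pre-Study test no pregnancy check is scheduled before the repeat injections at Imaging 2 (up to 12 weeks after Imaging 1 by the calendar) or the optional Imaging 3 (up to 24 weeks), although pregnancy is a mandatory reason to discontinue. Second, footnote 1 conflicts with Section 6.2 on who must be tested at baseline. The second count rests on the ordinary meaning of childbearing potential.

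Two larger figures are tempting but not supported. Section 8.1 counts the second scan from the start of therapy and says "Patients will typically start the selected hormone targeted therapy within 30 days of the FES PET scan". Adding upper ends gives 30/7 + 12 = 16.3 weeks to the second scan and 16.3 + 12 = 28.3 weeks to the third. The therapy-start and second-scan windows are described as typical, so these sums are not maxima. Likewise, an assumed share of women of childbearing potential could be applied to the 20 patients (5% to 30% would give 0.05 × 20 = 1 to 0.30 × 20 = 6). The documents give no such share, and the result would count women who could become pregnant, not pregnancies exposed. The case rests on the missing check.

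This is a matter of patient safety and internal consistency. It should be corrected, but it leaves the sample size, power and analysis as they are.

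**What to change.** - In Appendix A, reword footnote 1 to match Section 6.2, so that all women of childbearing potential are tested at baseline.
- Extend the pregnancy row to Imaging 2 and Imaging 3. Require a negative result within a stated window before the study FES injection and any research FDG injection. FES and FDG are done on separate days (Section 14.0), so set the window to let one test cover both scans at a time point. The sponsor and investigator choose the test method and the window.
- Add the check to the Section 9.1 list of steps before FES administration.
- Leave a baseline FDG scan done as standard care outside the requirement.

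The cost is a calendar and text amendment and one simple test per repeat imaging time point, that is, one or two per patient at visits already scheduled. Patients now waived by footnote 1 also need a baseline test. Only women of childbearing potential are affected.

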12.0 CONCOMITANT MEDICATIONS

Because interaction of < 5 µg of [18F]FES with other concomitantly administered drugs through the cytochrome P450 system or other pathways is extremely unlikely, this section is not applicable.

The infusion and imaging procedure will be terminated in any patient who exhibits adverse reactions as described in section 4.

13.0 ADVERSE EVENTS

13.1 Adverse Event

According to ICH guidelines (Federal Register. 1997; 62(90):25691-25709) and 21 CFR 312.32, IND Safety Reports, and ICH E2A, Definitions and Standards for Expedited Reporting, an adverse event is defined as follows:

An adverse event is any untoward medical occurrence in a clinical investigation subject administered a medicinal product and which does not necessarily have a causal relationship with this treatment. An AE can therefore be any unfavorable and unintended sign (including an abnormal laboratory finding), symptom, or disease temporally associated with the use of a medicinal product, whether or not considered related to the medicinal product.

Abnormal laboratory values for laboratory parameters specified in the study should not be recorded as an adverse event unless an intervention is required (repeat testing to confirm the abnormality is not considered intervention), the laboratory abnormality results in a serious adverse event or the adverse event results in study termination or interruption/discontinuation of study treatment.

Medical conditions present at screening (i.e., before the study treatment is administered) are not adverse events and should not be recorded on adverse event pages of the CRFs. These medical conditions should be adequately documented on the subject chart. However, medical conditions present at baseline that worsen in intensity or frequency during the treatment or post-treatment periods should be reported and recorded as adverse events.

13.2 Serious Adverse Event

An adverse event should be classified as an SAE if it meets one of the following criteria:

Table 13.1: SAE Criteria

Fatal	Adverse event results in death.
Life threatening:	The adverse events placed the subject at immediate risk of death. This classification did not apply to an adverse event that hypothetically might cause death if it were more severe.
Hospitalization:	It required or prolonged inpatient hospitalization. Hospitalizations for elective medical or surgical procedures or treatments planned before enrollment in the treatment plan or routine check-ups are not SAEs by this criterion. Admission to a palliative unit or hospice care facility is not considered to be a hospitalization.
Disabling/incapacitating	Resulted in a substantial and permanent disruption of the subject's ability to carry out normal life functions.
Congenital anomaly or birth defect:	An adverse outcome in a child or fetus of a subject exposed to the molecule or treatment plan regimen before conception or during pregnancy.
Medically significant:	The adverse event did not meet any of the above criteria, but could have jeopardized the subject and might have required medical or surgical intervention to prevent one of the outcomes listed above.

